5.8.3. Main Analytical Approach

Primary efficacy endpoint will be summarized using descriptive statistics by treatment group and visit, if appropriate. Statistical comparisons for each endpoint will be constructed without adjustment for multiplicity.

The RRatio will be analyzed using an analysis of covariance (ANCOVA) model including treatment and the baseline seizure frequency per week as a covariate. The differences between the treatment dose group and placebo will be estimated based on the least square mean (LSMean) difference between each CVL-865 dose group vs placebo and combined CVL-865 dose groups vs placebo with corresponding 90% confidence interval (CI) and P-value.

5.8.4. Sensitivity Analyses

5.8.4.1. Treatment Effect based on Actual Treatment Received

Should a discrepancy between the study treatment received and the randomized treatment assignment occurred in 4 or more subjects, a sensitivity analysis may be conducted based on the study treatments that subjects actually received using the analysis method described in Section 5.8.3.

5.8.4.2. Impact of Low eDiary Entry Compliance

To evaluate the impact of subject's low compliance of eDiary entry on the results from the main analysis, a sensitivity analysis that treat these cases as missing at random will be performed. Specifically, if a subject has more than 50% of their diary entries missing over a period (baseline, maintenance, etc), the seizure frequency for that period will be treated as missing. Multiple imputations under missing at random assumption will be performed. The Markov chain method implemented in SAS PROC MI will be utilized based on the mITT population. The imputations will be performed on the logarithmic scale $(\ln(X+1))$, where X represents the 7 day average seizure frequency for a period, and back transformed to conform to the multivariate normality distribution and the imputed values will then be back transformed to the original scale. SAS PROC MI will be used to generate 10 possible imputed datasets using the following SAS code:

```
proc mi data=mcmc1 seed=SEED1 nimpute=10 minimum=0 out=Out1X;
mcmc chain=multiple displayinit initial=em(itprint);
var TRT y0 y;
run;
```

Where TRT is an indicator variable representing treatment with the two treatment groups of 'CVL-865 7.5 mg BID', 'CVL-865 25 mg BID' or 'Placebo', y represents $\ln(7 \text{ day average}$ seizure frequency over maintenance period + 1), y0 is $\ln(7 \text{ day average seizure frequency over}$ the baseline period+1), and SEED1 is a random number.

Each of these datasets will be analyzed using the same ANCOVA model through SAS PROC MIXED as described in Section 5.8.3. The results of the analyses of the datasets will be combined using PROC MIANALYZE to produce an inferential result.

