1.2. Sample Size Considerations

Approximately 214 subjects will be screened to achieve 150 subjects randomly assigned to treatment (50 per group) and 120 evaluable subjects for an estimated total of 40 evaluable subjects per treatment group.

A sample size of 50 subjects per group (total of 150 subjects) will provide at least 80% power to detect a difference in the means of the primary outcome measure (RRatio) of -20 (PASS 2008 Tests of Two Means, Two Sample T-Test, 2-sided alpha level = 0.1, Standard Deviation=34, and a 20% dropout rate). Approximately 214 subjects will be screened to achieve 150 subjects randomized.

In the event of higher than anticipated early terminations due to COVID-19 or other reasons, Cerevel may extend enrollment in order to maintain the planned statistical power.

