1.3. Measures to Minimize Bias: Randomization and Blinding

1.3.1. Subject Assignment to Treatment

All subjects will be centrally randomized in a 1:1:1 ratio to 3 treatment arms (CVL-865 7.5 mg BID, 25 mg BID, or placebo) at the Visit 1 (Day 1) via an Interactive Voice Response System/Interactive Web Response System (IVRS/IWRS), according to a computer generated randomization scheme generated by a non-study statistician and be kept strictly confidential. Subjects will be sequentially assigned to the next available randomization number and will receive the IMP that corresponds to that randomization number. Once a randomization number has been assigned, it will not be reassigned.

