5.8.5. Subgroup Analyses

The mITT population is defined as all randomized subjects who receive at least 1 dose of IMP and have both an eDiary baseline compliance $\geq 20\%$ and at least 1 post baseline entry in the seizure diary during maintenance phase. To further assess the impact of the eDiary compliance, sensitivity analyses based on the subgroup with a baseline compliance $\geq 50\%$ and a maintenance phase compliance $\geq 50\%$ may be conducted if the sample size allows.

In addition, the following subgroup analyses will be conducted:

- 1. subjects with baseline eDiary compliance $\geq 80\%$.
- 2. subgroup analysis of baseline disease characteristics based on seizure frequency, defined: Low frequency= up to 20 seizures a week; High frequency = 21 and above, including all subjects with "uncountable" seizures will be conducted.

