5.9. Key Secondary Efficacy Analyses

5.9.1. Derivation of Key Secondary Efficacy Endpoints

5.9.1.1. Change in Log-Transformed Seizure Frequency from Baseline

The 7-day adjusted seizure frequency will be log-transformed using the convention ln(X+1), where X represents the focal onset seizure frequency. This will be summarized for the Titration Phase and Maintenance Phase.

5.9.1.2. 50% Responder

Responder status (yes or no) for a subject is determined by the percent reduction in 7-day adjusted seizure frequency during the Maintenance Phase from Baseline. A subject is defined as

a 50% responder if subject has at least a 50% reduction in the focal onset seizure frequency during the Maintenance Phase relative to the Baseline Period.

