5.9.4. Sensitivity Analyses

The sensitivity analyses to assess the impact of low eDiary compliance and that of discontinuation potentially related to treatment described in Section 5.8.4 for the primary estimand will also be performed for the key secondary efficacy estimand.

Two additional sensitivity analyses will be performed to assess the impact of the logarithmic transformation ln(X+1) of seizure frequency. The first one will be based on a slightly modified logarithmic transformation ln(X+0.1). This sensitivity analysis is to assess if the correction for zero in seizure frequency may have undue effect on other low seizure frequencies. In addition, the percent change from baseline in seizure frequency in Titration Phase and Maintenance Phase will also be analyzed using a nonparametric approach (in the original scale) of Wilcoxon rank sum test followed by the Mann-Whitney test for the comparison of each active treatment group to placebo.

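### The low-diary-compliance imputation in SAP 5.8.4.2 uses essentially the ANCOVA's own covariates, so for missing Maintenance periods it nearly repeats dropping those subjects and cannot reflect diary stopping that follows early response

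*SAP*

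**What the plan says.** SAP 5.8.4.2 applies to any subject with more than 50% of diary entries missing in a period, and it names baseline as well as Maintenance. For that subject, "the seizure frequency for that period will be treated as missing. Multiple imputations under missing at random assumption will be performed". The PROC MI step lists three variables: TRT, y0 (log baseline rate) and y (log Maintenance rate). Each completed dataset then goes through the ANCOVA of SAP 5.8.3, which models RRatio on treatment and baseline weekly frequency.

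Four other places bear on this:

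- **Main analysis.** SAP 3.1.1 divides the seizure count by the days with non-missing counts. The primary estimate therefore uses whatever days a low complier did record.
- **Compliance subset.** SAP 5.8.5 allows "sensitivity analyses based on the subgroup with a baseline compliance" of at least 50%, with the same threshold in Maintenance, if the sample size permits.
- **Titration data.** SAP Table 3 defines a Titration Phase seizure frequency, and 5.9.1.1 says of the log-transformed rate: "This will be summarized for the Titration Phase and Maintenance Phase".
- **Key secondaries.** "The sensitivity analyses to assess the impact of low eDiary compliance" are carried to the first key secondary endpoint in 5.9.4, and likewise to the responder rate in 5.10.3.

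Neither document gives an expected rate of low compliance or a pattern by arm.

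**The concern.** A sensitivity analysis for poor diary compliance should show whether the main result depends on what low compliers failed to record. If the imputation model contains only predictors that the analysis model already has, the imputed outcomes carry no new information. The answer is then close to a complete-case ANCOVA with some simulation noise.

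The assumption that matters most for a self-reported diary is whether people stop recording because of how they are responding. This analysis cannot reflect that, because no on-treatment seizure information enters for a subject whose Maintenance rate is blanked. Agreement between this analysis and the compliance subset could then be read as two independent confirmations when it is largely one. The same imputations support the robustness statements for the primary endpoint and both key secondary endpoints.

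**Working it through.** **1. The plan's own figure.** SAP 1.2 claims "at least 80% power to detect a difference in the means of the primary outcome measure (RRatio) of -20", with "2-sided alpha level = 0.1, Standard Deviation=34, and a 20% dropout rate" and "120 evaluable subjects for an estimated total of 40 evaluable subjects per treatment group". Standard error = 34 × √(2/40) = 7.60, and noncentrality = 20/7.60 = 2.63. The noncentral t power at two-sided 0.10 is 0.832. The exact t-test needs 37 per arm for 80%, and 40/(1 − 0.20) = 50. The stated power holds. It also gives a scale: the standard error of one contrast is about 7 points.

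**2. Predictors side by side.** The ANCOVA uses treatment and baseline rate. The imputation of y uses treatment and ln(baseline rate + 1). Only the scale differs.

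**3. Stopping driven by early Maintenance response.** Assumptions: 50 per arm; log-normal baseline rate; mean RRatio about −15 on placebo and −35 on both doses; RRatio SD about 33 (plan: 34); treatment entered as two indicators; 10 imputations; 1,500 trials per scenario. A subject with RRatio above −5 in Maintenance weeks 1 to 3 stops the diary after week 3 with probability p, leaving 5/8 = 62.5% of entries missing. Results for 25 mg versus placebo:

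| p placebo / active | % blanked placebo / 25 mg | Full data | Main analysis | Drop subjects | Planned MI | Planned MI − full |
|---|---|---|---|---|---|---|
| 0.3 / 0.3 | 11.7 / 6.0 | −20.16 | −20.26 | −18.75 | −18.77 | +1.39 |
| 0.5 / 0.5 | 19.5 / 10.1 | −20.09 | −20.21 | −17.24 | −17.31 | +2.78 |
| 0 / 0.3 | 0 / 6.1 | −20.43 | −19.95 | −23.23 | −22.87 | −2.44 |
| 0.1 / 0.3 | 3.9 / 5.8 | −19.97 | −19.69 | −21.36 | −21.15 | −1.18 |
| 0.3 / 0.53 | 11.8 / 10.7 | −20.20 | −19.97 | −21.13 | −20.92 | −0.72 |

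Planned MI tracks dropping subjects, and the main analysis stays within 0.5 points of full data. Under a common rule the shift is toward the null: an effective drug leaves more poor early responders on placebo, so placebo loses more of them. A shift toward the drug appears only where p is higher on active treatment. More extreme inputs widen the range. Stopping on active arms only at p = 0.5 moved the estimate 5.6 to 5.7 points from the main analysis toward the drug. Stopping mainly on placebo (0.3 / 0.1) moved it 3.8 points toward the null.

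**4. Stopping driven by Titration response.** Assumptions: 48 per arm, persistent subject-level log-rate shift SD 0.6, Titration showing 50% or 80% of the response, 800 trials per scenario. The correlation of planned MI with dropping subjects was 0.986 to 0.997. Bias was +0.7 to +1.9 under a common rule. It was −1.1 to −2.6 when poor responders on active treatment stopped more often, including −1.1 at near-equal overall rates (12% placebo, 13% active).

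**5. Adding ln(Titration rate + 1).** In the setting of step 4 it left at most 0.5 points of bias, and RMS error against the full-data estimate fell, for example from 3.2 to 2.2. A further 14 scenarios (500 trials each, 48 per arm) covered random, Titration-driven and early-Maintenance-driven stopping. The correlation of planned MI with dropping subjects was 0.986 to 0.994, and RMS error fell in all 14:

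- random non-compliance: 2.25 to 2.03, and 2.15 to 1.81;
- one case of stopping driven by early Maintenance response: 4.41 to 2.95.

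**6. Blanked baseline.** The mITT definition admits baseline compliance from 20%, so y0 can be imputed from an observed y. With 8% of baselines missing at random, imputing and dropping agreed on average (25 mg: −20.50 and −20.48) but differed by about 1.4 points (SD) per trial. Near-equivalence does not apply to these subjects.

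**The case against.** A reader might infer four stronger things. The documents support none of them.

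- **That the primary result is biased.** It is not touched. SAP 3.1.1 and 5.8.3 use the recorded days of low compliers; only a supporting estimate moves.
- **That diary stopping by poor responders flatters the drug.** That needs an extra assumption: more stopping on active treatment at equal response. Nothing in the documents supports or excludes it, and a common rule gives the opposite sign.
- **That 5.8.4.2 is wholly redundant with 5.8.5.** The subset is optional while the imputation is committed, and the two differ where the baseline is blanked.
- **That the Titration rate repairs everything.** Showing that it removes bias when Titration response drives stopping is partly circular. With stopping tied to early Maintenance response, one check gave −19.1 planned, −19.2 with Titration and −20.5 true. Another gave −16.7, −17.2 and −19.7. Recorded Maintenance weeks 1 to 3 brought the estimate within about 0.15 points of full data, but in that model those weeks were what drove stopping.

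It is also fair to say that high rates of low compliance may not occur. The schedule reviews the eDiary at every visit and contact after Screening, and Protocol 7.3 lists failure to comply with trial procedures as a reason to discontinue. SAP 5.7.1 counts only actual participation, so early dropout alone does not make a low complier. The SAP calls the study exploratory and labels this analysis missing at random. These points limit the size of the problem. They do not give the imputation any on-treatment information.

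**Conclusion.** The point holds as a weakness of one sensitivity analysis. For missing Maintenance periods, 5.8.4.2 adds little beyond dropping the subject and cannot reflect stopping related to early response. The jump-to-reference analysis in 5.8.4.3 does not cover this, because it concerns discontinuation for listed reasons.

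Under plausible assumed rates the sensitivity estimate can be off by roughly 1 to 3 RRatio points in either direction. That is 5% to 15% of the planned 20-point difference (1/20 and 3/20), and well under one standard error. Larger shifts need stronger arm imbalance than anything the documents suggest. The sizes depend on assumed compliance rates, an assumed link between response and stopping, and treatment entered as two indicators. The SAP writes TRT as one variable, which is a separate matter. With purely random non-compliance there is no bias, only lost precision.

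**What to change.** Add ln(Titration Phase 7-day rate + 1) to the PROC MI variable list in SAP 5.8.4.2, alongside y0 and y, as an auxiliary variable only. Leave the ANCOVA unchanged. Use the same imputation model for the low-compliance analyses in 5.9.4 and 5.10.3. State whether the 50% rule also blanks the Titration rate; where it is missing, the MCMC step imputes it with the rest.

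The cost is one more variable, already derived under Table 3, which may itself be missing for some subjects. No new data are needed. The text should also say that the analysis remains missing at random and only partly addresses stopping that follows early Maintenance response.

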1.1. Study Overview

This is a double-blind, parallel-group, placebo-controlled trial with subjects randomized to 1 of the following 3 arms in a 1:1:1 ratio:

- CVL-865 25 mg BID maintenance
- CVL-865 7.5 mg BID maintenance
- Placebo

This maximum duration is to be approximately 25 weeks, consisting of the following:

- 8-week Screening/Baseline Period
- 10- or 13-week Treatment Period, including an initial 2-week Titration Phase, an 8-week Maintenance Phase, and a 3-week Taper Phase (only for subjects not continuing treatment in the open-label extension trial). The tablets (including the number of tablets given) will be the same between the placebo and both CVL-865 dose arms during the Titration, Maintenance, and Taper Phases to maintain the blind
- 4-week Follow-up Period (only for subjects not continuing treatment in the openlabel extension trial)

Subjects are to continue on their current AEDs at the same dosages throughout the Screening/Baseline Period. If a subject has a vagus nerve stimulator (VNS), a deep brain stimulator (DBS), or a responsive neurostimulator (RNS), the settings must remain stable throughout the Screening/Baseline Period.

During this Screening/Baseline Period, subjects will be required to complete electronic seizure diaries (eDiary) and record all seizures in the eDiary for each day and days free of seizures. The presence or absence of all seizure types experienced by each subject will be recorded daily in the eDiary.

Subjects who satisfy all inclusion/exclusion criteria and thus are eligible for the trial will be randomized to 1 of 3 treatment arms at Visit 1 (Day 1). The daily dosing schedule will start at Day 1 with a 2-week Titration Phase during which time the subject's dose will be increased in a blinded fashion up the randomized dose level (CVL-865 25 mg BID, CVL-865 7.5 mg BID, or placebo). In the high-dose group, CVL-865 will be administered as

during the Titration Phase, and then 25 mg BID during the 8-week Maintenance Phase. In the low-dose group, CVL-865 will be administered as

during the Titration Phase, and then

7.5 mg BID during the 8-week Maintenance Phase.

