5.8.4.3. Impact of Discontinuation Potentially Related to Treatment

The seizure frequency data of subjects who discontinue of from the trial on or before Week 6 (Visit 3) for the following reasons are potentially missing not at random (MNAR).

- AE with AEHLGT eq 'Seizures (incl subtypes)'
- WITHDRAWAL BY SUBJECT
- LACK OF EFFICACY
- LOST TO FOLLOW-UP

In this assessment, the subjects with MNAR (to be identified and documented in Section 9.5 before database lock) will be imputed by jump to reference approach.

Specifically, the missing values in each of the active group will be imputed using the multiple imputation procedure described above except that the missing observations in CVL-865 group are not constructed from the observed data in the respective groups, but rather from the observed data in the placebo group. Any missing data from the placebo group is imputed using the observed data from the placebo group. The data will be log transformed using convention log(X+1) and back transformed to conform to the multivariate normality distribution. The

proc mi data = mcmc1 (where=(((y = . or y0=.) and trt ne 'Placebo') or (trt='Placebo' and (y0 ne. and y ne .)))) seed = SEED1 nimpute = 10 minimum =0 minmaxiter = 1000 out= Out1X; mcmc chain = multiple displayinit initial=em(itprint); var y0 y; run;

Where y represents $\ln(7 \text{ day average seizure frequency over maintenance period + 1})$, y0 is $\ln(7 \text{ day average seizure frequency over the baseline period+1})$, and SEED1 is a random number. Each of these datasets will be analyzed using the same ANCOVA model through SAS PROC MIXED as described in Section 5.8.3. The results of the analyses of the datasets will be combined using PROC MIANALYZE to produce an inferential result.

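### SAP 5.8.4.2 puts three arms into the low-compliance imputation model as one undefined TRT term, so this sensitivity analysis can shift with the coding a programmer chooses

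*SAP*

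**What the plan says.** SAP 1.1 has subjects "randomized to 1 of the following 3 arms in a 1:1:1 ratio". SAP 5.8.4.2 sets a period's seizure frequency to missing when more than half of its diary entries are absent. It then imputes on the ln(X+1) scale with the MCMC method of PROC MI, 10 imputations, relying on multivariate normality. The VAR list has three members: TRT, the baseline log rate y0 and the maintenance log rate y. TRT is explained in these words: "Where TRT is an indicator variable representing treatment with the two treatment groups of 'CVL-865 7.5 mg BID', 'CVL-865 25 mg BID' or 'Placebo". No coding follows.

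The jump-to-reference code in SAP 5.8.4.3 reads a dataset of the same name, mcmc1, and selects records with the condition "and trt ne 'Placebo') or (trt='Placebo' and". There, trt holds text.

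The imputed datasets go into the ANCOVA of SAP 5.8.3, which contrasts each dose, and the two doses combined, with placebo. The check is reused for the first key secondary endpoint in SAP 5.9.4 ("The sensitivity analyses to assess the impact of low eDiary compliance") and for the 50% responder rate in SAP 5.10.3.

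**The concern.** One indicator distinguishes two groups, not three. In a multivariate normal model every listed variable is a numeric component, so a variable holding arm names cannot be used. A programmer who meets this must invent a number for each arm, and the number matters. The model imputes y from a straight line in TRT, so whichever arm has the middle code is imputed towards the midpoint of the other two. A 0/1 active-versus-placebo code would impute both doses towards a common mean.

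The analysis exists to show whether poor diary compliance moves the result. If coding alone can move a dose contrast, a reader could attribute the shift to non-compliance. Leaving the code to be chosen at programming also means the analysis is not fully prespecified.

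**Working it through.** **The plan's own yardstick.** Inputs from SAP 1.2: "difference in the means of the primary outcome measure (RRatio) of -20", with "PASS 2008 Tests of Two Means, Two Sample T-Test, 2-sided alpha level = 0.1, Standard Deviation=34, and a 20% dropout rate" and "120 evaluable subjects for an estimated total of 40 evaluable subjects per treatment group". The standard error of a difference is 34 × √(2/40) = 7.60. Power is Φ(20/7.60 − 1.645) = Φ(0.986) = 83.8% (83.2% with the t distribution). This agrees with the SAP: "A sample size of 50 subjects per group (total of 150 subjects) will provide at least 80% power". The point does not depend on this figure; it supplies the scale of 20 points for the design effect and 7.6 for the standard error.

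**Closed form.** Let p be the share of maintenance values imputed, equal in all arms. A contrast after imputation is about (1 − p) × true contrast + p × contrast implied by the imputation model, so

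bias ≈ p × (implied contrast − true contrast).

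With balanced arms and equally spaced codes, the least-squares line has slope (mean of last-coded arm − mean of first-coded arm)/2 per code step.

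Two examples, with true effects 0 (placebo), 0 (7.5 mg), −20 (25 mg):
- Dose order (placebo 0, 7.5 mg 1, 25 mg 2): slope = (−20 − 0)/2 = −10. Implied contrasts with placebo are −10 for 7.5 mg and −20 for 25 mg. Bias is −10p and 0.
- Order of the labels in 5.8.4.2 (7.5 mg 1, 25 mg 2, placebo 3): slope = (0 − 0)/2 = 0. Both implied contrasts are 0. Bias is 0 for 7.5 mg and +20p for 25 mg.

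Bias in RRatio points at p = 10/20/30%:

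| Coding | True effects (placebo / 7.5 / 25 mg) | 7.5 mg vs placebo | 25 mg vs placebo |
|---|---|---|---|
| Dose order | 0 / 0 / −20 | −1 / −2 / −3 | 0 |
| Dose order | 0 / −20 / −20 | +1 / +2 / +3 | 0 |
| Dose order | 0 / −10 / −20 | 0 | 0 |
| Label order | 0 / 0 / −20 | 0 | +2 / +4 / +6 |
| Label order | 0 / −10 / −20 | 0 | +1.5 / +3 / +4.5 |
| Active vs placebo | 0 / 0 / −20 | −1 / −2 / −3 | +1 / +2 / +3 |

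**Simulation.** The imputation is on the log scale and truncated at zero, so the closed form is approximate. I simulated the full sequence: normal-model imputation of y, 10 imputations, back-transformation, ANCOVA of RRatio. Assumptions not in the documents: 50 per arm with data, placebo mean RRatio −10, log-ratio SD 0.80 (RRatio SD about 33–35), log-normal baseline with median about 4 per week, baseline observed, maintenance values missing completely at random. Bias relative to two dummies, at 10/20/30%:
- Dose order, 25 mg effect only: 7.5 mg −0.9/−1.8/−2.9; 25 mg within 0.1.
- Dose order, plateau: 7.5 mg +0.9/+1.9/+2.7; 25 mg at most +0.2.
- Dose order, linear: at most 0.3 for either dose.
- Active vs placebo, 25 mg effect only: 7.5 mg −0.9/−1.9/−2.7; 25 mg +0.9/+1.9/+2.8.
- Label order, 25 mg effect only: 25 mg estimates −18.2/−15.6/−14.0 against −19.9/−19.2/−18.6 with dummies, a loss of 1.7/3.6/4.6. With baseline about 3 per week: −17.7/−15.5/−13.8 against −19.8/−19.7/−20.1, a loss of 2.1/4.2/6.3.
- Label order, linear: −18.2/−16.5/−15.1 against −19.4/−19.0/−19.1, a loss of 1.2/2.5/4.0.

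Two dummies stayed within about 1 point of the full-data estimate.

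**The case against.** The strongest reply is that the SAP leaves the code unspecified and does not prescribe a bad one. The order of labels in a sentence is not a numeric code, and the order varies: SAP 1.1 lists 25 mg first, SAP 1.3.1 lists 7.5 mg first. Under the natural dose order, 25 mg against placebo is almost untouched. Protocol 4.3 anticipates a submaximal effect at 7.5 mg, not a null one, and with a linear pattern dose-order coding does no harm. The wording about an indicator and two groups could also mean separate runs of each dose against placebo, where a 0/1 TRT is valid. All of this stands as a limit on the size. It does not rescue the text: separate runs are not specified, and the code shown has one run with three arms.

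The imputed share is unknown. Compliance under SAP 5.7.1 counts only time in the study, so the 20% dropout rate is no guide to it. At 5% imputed, the 10% figures roughly halve.

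If TRT is text, the program should stop visibly and bias nothing. That is fair, but the repair would still be an unplanned choice. Independent programming (SAP 9.7) checks execution and does not settle an ambiguous specification.

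Low compliance is also examined without imputation in SAP 5.8.5, and SAP 5.4 calls the trial exploratory. Both points lower the stakes.

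**Conclusion.** The specification in SAP 5.8.4.2 is defective. Three arms enter a multivariate normal imputation as one term described as covering two groups. As written, the term is either unusable text or a single number that constrains the arm effects. Only separate dose-versus-placebo runs, which the SAP does not describe, would make one 0/1 indicator valid.

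The bias is conditional. With 10–30% imputed and an effect of −20 at 25 mg only, it is about −1 to −3 points on 7.5 mg (dose order) or a loss of about 2 to 6 points on 25 mg (label order). It is essentially nil with dose order and a linear dose-response. Six points is 30% of the design effect and about 0.8 of the planning standard error (6/7.6). The share imputed, the dose-response shapes and the codings are all assumptions.

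A reader might infer that this analysis is bound to understate 25 mg, or that the primary result is biased. The documents support neither. No coding is stated, and the main ANCOVA in SAP 5.8.3 and the main key secondary analyses (5.9.3, 5.10.2) do not use the imputation. The jump-to-reference code in 5.8.4.3 does not have TRT in its VAR list. The fault lies in one sensitivity analysis, reused for both key secondary endpoints. It should be fixed, but no primary conclusion rests on it.

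**What to change.** In SAP 5.8.4.2, change two groups to three, and replace TRT in the VAR list with two 0/1 variables, one for 7.5 mg and one for 25 mg, both 0 for placebo. Alternatively, impute separately by arm. State the chosen form in the text, and have 5.9.4 and 5.10.3 refer to it. If trt stays as text in mcmc1 for 5.8.4.3, derive the two dummies alongside it.

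The cost is a few lines of SAP text and code before database lock, with no new data and no design change. More imputations, or titration-phase frequency as an auxiliary variable, would be optional refinements; neither addresses this error.
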